**Version Number: V. 4.0**

**Feb. 18, 2022**

## Statement of Compliance

The trial will be carried out in accordance with International Conference on Harmonisation Good Clinical Practice (ICH GCP) and the following:

- United States (US) Code of Federal Regulations (CFR) applicable to clinical studies (45 CFR Part 46, 21 CFR Part 50, 21 CFR Part 56, 21 CFR Part 312, and/or 21 CFR Part 812)

USANA Health Sciences (USANA)-funded investigators and clinical trial site staff who are responsible for the conduct, management, or oversight of USANA-funded clinical trials have completed Human Subjects Protection and ICH GCP Training.

The protocol, informed consent form(s), recruitment materials, and all participant materials will be submitted to the Institutional Review Board (IRB) for review and approval. Approval of both the protocol and the consent form must be obtained before any participant is enrolled. Any amendment to the protocol will require review and approval by the IRB before the changes are implemented to the study. In addition, all changes to the consent form will be IRB-approved; a determination will be made regarding whether a new consent needs to be obtained from participants who provided consent, using a previously approved consent form.

# 1. Protocol Summary

## 1.1 Synopsis

Title	A Follow-up Trial of Proglucamune® in the Treatment of Protective Qi Insufficiency, a TCM Condition
Study Description:	In this protocol, we will developed a novel, evidence-based approach to test the hypothesis that $\beta$ -glucan enhances Protective Qi (PQi), an important TCM concept which stipulates that a protective force circulates throughout the body surface and works as the first line of defense of against “external pernicious influences (外邪)”.
Objective:	The primary objective of this study is to re-test the beneficial effects of Reishi for its Protective Qi (PQi) enhancing and immune-modulating effects in a double-blind, placebo-controlled study. The secondary objective of this study is to determine the effect of Proglucamune® on strengthening General Qi (GQi).
Endpoints	The primary endpoint is the change of PQi Deficiency (PQD) status accessed by a standardized multifactorial severity score and traditional method. The secondary endpoint is the change of GQi Deficiency (GQD) status accessed by a standardized multifactorial severity score and traditional method, the change of Global Health, Emotional Impact, Saliva sIgA, and Emotional and Behavioral Dyscontrol.
Study Population	130 male or females aged 18 to 65 will be enrolled without regard to race or ethnic background. All subjects should be generally healthy but exhibit an PQi Insufficiency score >1.8 (an empirical threshold derived from preliminary study that allows increased responsiveness to beta glucan).
Description of Sites/Facilities Enrolling Participants:	This study will be conducted at the Elegant and Olive Health Clinic, [name]. Subjects for this study will be recruited through investigators of this trial, referral from other TCM practitioners, or via advertisement.
Description of Study Intervention:	Participants will be treated with 2 tablets of Proglucamune per day (containing 200mg of beta glucan).
Study Duration:	24 months
Participant Duration	3 months

## **2. Introduction**

### **2.1 Study Rationale**

TCM has developed a number of medicinal treatments to strengthen the PQi. Among these is the use of Reishi mushrooms, either alone or in combination with other TCM remedies. Although there are no definitive data on the treatment duration of Reishi or Reishi-containing formulas needed to improve PQi, anecdotal reports claim significant improvement within days. Notably, Western medicine has identified immune-boosting properties of Reishi, which may explain the PQi enhancing effects of this plant. Specifically,  $\beta$ -glucan – a component of Reishi - has been shown to activate macrophages [1-3], neutrophils [4, 5) and other immunocytes [6-8], and may exhibit particular benefits among macrophage-rich organs such as the lung, liver and spleen. In fact,  $\beta$ -glucans from sources other than Reishi, such as the baker's yeast, are able to initiate similar immune responses and clinical benefits [9].

### **2.2 Background**

Qi is a central concept of traditional Chinese medicine (TCM) and was first documented in the oldest TCM writings more than 2000 years ago. Generally speaking, Qi refers to the vital energy of the body and is derived from two primary sources: 1) inborn Qi (that may be construed as genetics), and 2) pectoral Qi (can be construed as metabolism). Moreover, Qi manifests itself in two forms: Nutritive Qi and Protective Qi (PQi), which can be understood to reflect an individual's nutritional state and immune health, respectively. Regarding the latter, PQi functions to defend the body from the invasion of external pathogens. In this context, PQi is analogous to the anatomical barriers and immune cells of the innate immune system located for example, at the mucosal surfaces of the respiratory and digestive tract.

According to TCM, a Protective Qi Deficiency (PQD) manifests as a predisposition to cold\* (\*, as defined in TCM), susceptibility to wind\* (that carries pathogens), abnormal sweating, and fatigue. Clinical examination of individuals with PQi reveals a feeble or weak pulse as well abnormal tongue features such as the appearance of a thin whitish coating, atypical thickness, and uncharacteristic teeth marks on the side. The individual's face often lacks gloss. Notably, these manifestations are mild, may happen to many people and, from the perspective of western medicine, may not in fact warrant diagnosis of an individual as being sick. If left untreated however, TCM indicates that a worsening of symptoms may ensue, such as the onset of coughing, fever, headache, delirium,

bleeding, etc. In this regard, the identification of an individual with PQD is viewed as an aspect of disease prevention in TCM.

## 2.3 Risk/Benefit Assessment

### 2.3.1 Known Potential Risks

The risk of this trial is minimal due to the established safety profile of the active ingredients (beta glucan), which has been approved by FDA as a GRAS (Generally Considered As Safe) ingredient. In addition, the test formula has been used in market by the public for several years without adverse effects reported.

### 2.3.1 Known Potential Benefits

The finding of PQi-enhancing effect in PQD patients will avail TCM practitioner to prescribe PQD therapy based on principles of evidence-based medicine.

## 3. Objectives and Endpoints

Objective	Endpoints	Justification for endpoints
Primary		
To test $\beta$ -glucan enhances Protective Qi (PQi)	
 
• PQi Deficiency (PQD) status accessed by a standardized multifactorial severity score
 
• PQi Deficiency (PQD) status accessed by a traditional method
 
	
We have previously created and validated standardized score for assessing PQD severity.
 
The traditional diagnosis method is also used as an additional way to evaluate the treatment.

Secondary		
To evaluate the effect of $\beta$ -glucan on GQi severity score, salivary IgA, general health status through Patient-Reported Outcomes Measurement Information System (PROMIS), Emotional Impact, and Emotional, and Behavioral Dyscontrol.	
 
• GQi Deficiency (GQD) status accessed by a standardized multifactorial severity score
 
• GQi Deficiency (GQD) status accessed by a traditional method
 
• Global Health - Physical
 
• Global Health – Mental
 
• Emotional Impact
 
• Saliva sIgA
 
• Emotional and Behavioral Dyscontrol
 
	
PQi is a component of GQ, <math>\beta</math>-glucan may improve GQi, too.
 
Salivary IgA is a biomarker of immune. <math>\beta</math>-glucan's effect on immune defense may affect Salivary IgA.
 
The improvement of PQi can be accompanied by improved life quality.
 
Patient-Reported Outcomes Measurement Information System (PROMIS), Emotional Impact, Emotional and Behavioral Dyscontrol will be collected to evaluate the improvement of participants' life quality.

## 4. Study Design

## **4.1 Overall Design**

The objective of this study is to expand upon our previous findings and, more specifically, to re-test our hypothesis in a triple-blind, placebo-controlled study with n=62 subjects in both the intervention (Proglucamune®) and placebo treatment groups. In addition, since TCM literature indicates that Reishi not only increases PQi but also the level of Qi in general (i.e., general Qi, GQi), and since PQi is a component of GQ, the secondary objective of this study is to determine the effect of Proglucamune® on strengthening GQi.

## **4.2 Scientific Rational for Study Design**

The overlap of TCM and western medicine concerning the beneficial effects of Reishi for its Qi enhancing and immune-modulating effects, respectively, has prompted us to investigate whether or not Reishi, in conjunction with other natural products used in TCM, can enhance an individual's PQi. In a preliminary study [10], we investigated this subject using a commercial product (Proglucamune®, USANA Health Sciences) in a one-group, pre-test post-test design (n=30 subjects). The results of that work support our hypothesis that Proglucamune®, a Reishi and  $\beta$ -glucan containing product, enhances PQi in individuals with PQD.

In this triple-blind, placebo-controlled study, the control group will be treated with placebo. For the placebo tablets, the active ingredients will be replaced with equivalent amount of excipients (microcrystalline cellulose), and coated with the same material as  $\beta$ -glucan. The appearance and taste of the placebo are the same as that of treatment tablet. It will be able to minimize the influence of placebo effect.

## **4.3 Justification for Dose**

The dose regimen (2 tablets daily that contain ~200mg beta glucan) in the trial has been tested previously in our preliminary trial and found to be effective [10].

## **4.4 End of Study Definition**

A participant is considered to have completed the study if he or she has completed all phases of the study including the last visit shown in the Schedule of Activities (SoA), **Section 1.3**.

## **5. Study Population**

### **5.1 Inclusion Criteria**

1. Male or females aged 18 to 65 years (inclusive) without regard to race or ethnic background
2. Provide a signed Informed Consent prior to entry in the study.

3. Willing to follow all study instructions and consume the assigned investigational product for 12 weeks.
4. Not currently taking a  $\beta$ -glucan containing supplement or any other supplement that might interfere with the study design.
5. Ability to swallow tablets and pills.
6. Exhibit a PQD severity score  $> 1.8$  (calculated by Table 1 & Table 2)

## **5.2 Exclusion Criteria**

1. Persons diagnosed by TCM as having medical conditions that interfere with the status of PQi.
2. Significant acute or chronic illness or other medical conditions that will prevent or interfere with giving an informed consent, or with participation in the study.
3. Scheduling difficulties or lack of transportation that will prevent or interfere with their ability to attend all of the necessary study visits.
4. Persons medically diagnosed with depression or anxiety disorders.
5. Persons with a history of alcohol abuse or other substance abuse within the previous 2 years.
6. Females who are attempting to become pregnant, pregnant, lactating or who have given birth within 1 year.
7. Persons who have had a medical surgery in the past 4 weeks or have scheduled a surgery during the study period.
8. Persons currently enrolled in a clinical trial, or who have completed a clinical trial within the last 4 weeks.
9. Allergies to mushrooms or other fungi.
10. Significant problems with constipation or diarrhea.
11. A lifestyle or schedule incompatible with the study protocol.
12. Persons who are allergic to yeast products, have autoimmune disease/an immune disorder, or take antidepressants, blood thinners (anticoagulants, acetylsalicylic acid), or immunosuppressant medication

## **5.3 Lifestyle Considerations**

During this study, participants:

1. Must not have a lifestyle that will prevent or interfere with their ability to attend all of the necessary study visits
2. Must not have alcohol abuse
3. Must not use marijuana for recreational or medicinal purposes

## 5.4 Screening Failures

Individuals who do not meet the criteria for participation in this trial won't be enrolled.

## 5.5 Strategies for Recruitment and Retention

Subjects will be recruited through referral from other TCM practitioners and advertisement on social media. Individuals who were believed to have PQD by referring practitioners or by themselves will be encouraged to apply. Potential subjects recruited through TCM practitioners will not be referred without prior consent. All potential subjects will report to the TCM clinic for a screening visit (Visit 1, **Section 1.2**) prior to enrollment into the study. At screening, all potential subjects will be provided with an Information and Consent Form (ICF) and provided with sufficient time to read the ICF. Thereafter, a TCM practitioner will review the ICF with each potential subject and will address any questions the potential subject may have concerning the ICF and/or the clinical trial. The potential subject will also be provided with the option of taking the ICF home for review prior to making his or her decision to enroll or not enroll in the study. If potential subjects refuse consent, they will be asked to leave the clinic and will not be enrolled in the study. If they provide consent, the potential subject will sign the consent form, receive a duplicate for their own records, and will be considered as consented subjects.

Once consent has been obtained, a TCM practitioner will initiate the screening process (Appendix 1) that includes collection of information concerning anthropometric, general health status as well as PQi status. If the potential applicants exhibit a PQD severity score  $\leq 1.8$  (see Table 1 & Table 2), which, according to our preliminary study, represents less responsiveness to the treatment, they will be excluded from the trial, whereas the applicants with a score  $>1.8$  will begin the enrollment process.

Enrollment will be initiated by a TCM practitioner. Note that the enrollment process may occur on the same day as the Screening Visit, or at a date not more than 14 days from the Screening Visit. If enrollment is performed on the same day as the screening visit, the enrollment process will begin with a basic physical examination (to be conducted by the Qualified Investigator, Q.I.; see Appendix 2) immediately following the screening process and continue as outlined below. Note that subjects that complete screening and enrollment on the same day will be considered to have completed both the Screening Visit and Study Visit 1. However, if subject enrollment cannot be completed during the Screening Visit (i.e., due to time restrictions or other circumstances), subjects will return to the clinic within 14 days to initiate the enrollment procedure. During this visit (Study Visit 1), the TCM practitioner will re-assess the subjects' PQD status (Appendix 4). If the potential subject does not exhibit PQD, they will not be enrolled in the study. If the potential subject continues to exhibit PQD, they will continue the

enrollment process. (Note that for purposes of data analysis, subjects' PQD status characterized during Study Visit 1 will supersede their PQD status characterized during the Screening Visit). As outlined above, the enrollment process begins with a basic physical exam of the head, ears, eyes, nose, throat, etc. performed by the Q.I. If, in the estimation of the Q.I., the potential subject is deemed not to be in good general health, they will not be enrolled in the study. If potential participants are deemed to be otherwise healthy by the Q.I., the enrollment procedure will continue. The enrollment will start in Dec. 2018 and concluded in March 2019.

## **6. Study Intervention**

### **6.1 Study Intervention Administration**

#### **6.1.1 Study Intervention Description**

Proglucamune® lot No. AV2291 and Placebo lot No. AV2287.

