### **6.2.2 Formulation, Appearance, Packaging, and Labeling**

Placebo formula contain excipients (831 mg per tablet) and coating materials. The placebo excipients include microcrystalline cellulose 806mg, Pregelatinized Starch 10.7 mg, croscarmellose sodium 7.11 mg, silicon dioxide: 3.57 mg, and Ascorbyl Palmitate 3.57 mg.

Treatment formula contain active ingredients and excipients (846 mg per tablet) and coating materials.

The treatment active ingredients include Beta-Glucan Complex (Baker's Yeast Extract [Saccharomyces cerevisiae, cell wall]) 125 mg (The w/w yield of prepared extracts in terms of starting crude material: 38%), Reishi Mushroom [Ganoderma lucidum, whole mushroom powder] 125 mg, Shiitaki Mushroom [Lentinula edodes, whole mushroom powder] 25 mg, and Zinc (as Zinc Gluconate) 25mg.

The treatment excipients include Microcrystalline cellulose 426 mg, modified cellulose 90 mg, vegetable fatty acid 10 mg, croscarmellose sodium 5 mg, and silicon dioxide 5 mg, and Hydroxy Propyl Cellulose 9mg.

Treatment and placebo formula contain the same coating materials (Opadry II Complete Film Coating System 57U150022 Red).

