## **6.3 Measures to Minimize Bias: Randomization and Blinding**

This study will be a randomized, triple-blind, placebo-controlled, parallel arm design. The participants will be recruited and randomized in a 1:1 ratio to either of two interventions: 1) Daily consumption of the control supplement (placebo), and 2) Daily consumption of the treatment ( $\beta$ -glucan). For randomization, these participants will be first stratified based upon: 1) ethnicity, 2) whether or not the subject has had an influenza vaccine (flu shot) since October 1, 2018, and 3) whether or not the subject currently exhibit a 'cold' as defined by TCM (hereafter referred to as cold\*). These factors will be deemed potential confounders of  $\beta$ -glucan effect. Throughout the trial, including the recruitment and the treatment, all participants and on-site investigators will be blinded to treatment.

Each participant has an emergency envelop, the information of this participant's allocation (treatment group or placebo group) will be include in, and PI will hold onto the envelops. If any participant needs to be unblinded, PI will open the corresponding envelop and notice the relevant physician.

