#### **9.4.2 Analysis of the Efficacy Endpoint(s)**

Trial outcome measures, if they are continuous, will be evaluated by skewness and kurtosis for normality and expressed as mean (95% CI) if both measures were within the range of (2, -2); otherwise they will be expressed as median (95% CI) with specification. Given the potential effect of treatment time on trial outcomes, we will analyze the effect of  $\beta$ -glucan with adjustment by treatment time. This will be conducted by linear mixed regression [16] or Aligned Rank Transformation ANOVA [17] if assumptions of the regression model were not satisfied. Categorical outcomes will be derived from conventional PQD diagnosis. The effect of  $\beta$ -glucan will be analyzed using generalized mixed linear model [18] for conventional PQD diagnosis.

For all statistical analyses, differences with a  $P < 0.05$  (two tailed) will be considered significant.

Other details analysis of the primary endpoints are described as follows:

- The PQi status of each participant at baseline and each follow-up visit will be measured by on-site investigators (licensed TCM practitioners) through a standardized quantitative assessment (Table 1 & Table 2). Each health condition relevant to PQD (i.e. cold frequency, symptoms, and signs) will be scored on a designed scale (ranging 1-10, with higher number indicating more severe deficiency) based on a set of standardized and specified criteria (Table 2). The sub-scores are then weighted (cold history 25%, symptoms 33.3%, signs: 41.7%) to arrive at a final PQD severity score. This score is on a 1-5 scale, with 5 being the most severe deficiency. The change of the score from baseline, indicating the treatment effect, will be calculated and analyzed by statistical means.
- PQi status of each participant at baseline and each follow-up visit will be measured by on site-investigators (licensed TCM practitioners) through non-standardized, qualitative traditional assessment. The status was characterized by non-PQD or PQD. The change of PQi status from baseline, indicating the treatment effect, will be calculated and analyzed by categorical statistic.

Other details analysis of the secondary endpoints are described as follows:

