#### **10.1.5 Quality Assurance and Quality Control**

##### **10.1.5.1 Regulatory Compliance**

The investigators must agree to comply with the sponsor and regulatory requirements in terms of auditing of the study. This includes access to the source documents for source data verification at any time by the sponsor. In addition, the sponsor and investigators (as appropriate) will permit trial-related monitoring, audits, IRB/IEC review, and regulatory inspections and will allow direct access to source data and documents for these purposes. An initiation meeting will be conducted by the sponsor. At this meeting, the protocol and logistical aspects of the study will be reviewed by the Sponsor with the investigators and all study staff.

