##### **10.1.5.2 Data Monitoring**

Source documents will be reviewed during an audit performed by the sponsor at four to six weeks from the beginning of the study (i.e., as indicated by enrollment of the first participant) and at the conclusion of the study following the release of the final participant. This will be done to ensure that all data is being properly gathered and recorded in accordance with the manner specified in the protocol. The participant files will be reviewed to confirm that:

- Informed consent was obtained and documented;
- Enrolled participants fulfilled all inclusion criteria and did not meet any exclusion criteria;
- AE/SAE reporting has been performed as applicable;
- Study visits have been conducted as per protocol and information has been recorded in the appropriate place in the source document;
- The study product is being stored correctly and an accurate record of its dispensation to the study participants is being maintained (accountability).

Incorrect, inappropriate, or illegible entries in the participant files will be returned to the investigator for correction. No data disclosing the identity of participants will leave the study center. The Investigator and any designees will maintain confidentiality of all participant records.

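### Section 6.1.1 prints the lot-to-arm key in a protocol shared with site raters who are meant to be blinded, and no masking of lot numbers is described

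*Combined protocol and SAP*

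**What the plan says.** All places are in the combined protocol and SAP.

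- **The key.** Section 6.1.1 consists of two lot numbers, each tied to an arm: Proglucamune "lot No. AV2291 and Placebo lot No. AV2287".
- **Who is blinded.** Section 6.3 calls the trial triple-blind and says that "all participants and on-site investigators will be blinded to treatment". Each participant's allocation sits in an emergency envelope held by the principal investigator.
- **Who sees the protocol.** Section 10.1.5.1 says that at the initiation meeting "the protocol and logistical aspects of the study will be reviewed by the Sponsor with the investigators and all study staff".
- **Who rates.** Under section 9.4.2 the PQi status "will be measured by on-site investigators (licensed TCM practitioners) through a standardized quantitative assessment". The same practitioners make the second primary measure, PQD or non-PQD, "through non-standardized, qualitative traditional assessment".
- **Stock handling.** Section 6.2.1 has unused tablets collected and new ones given out at days 28 and 56. Section 10.1.5.2 has the sponsor's audit confirm that an accurate dispensing record is kept. Neither mentions lot numbers or says who does this work.
- **Labels.** Section 6.2.2 is headed "Formulation, Appearance, Packaging, and Labeling" but gives only composition and coating. It has no label content, kit code or masking rule, and no other section supplies one.

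**The concern.** A lot number is harmless to the blind as long as nobody at the site can translate it. Here the translation is printed in the document that site staff are taken through. Because each arm has a single lot, two numbers are enough to decode any participant whose lot is known.

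This matters because of what is being rated. Pulse, tongue and voice are the practitioner's own findings, and the traditional diagnosis has no written criteria. The documents describe no independent assessor and no check on whether blinding held. A rater who knew the arm, even without intending to use it, could shade these judgements in one direction, and the resulting difference would look like a treatment effect.

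**Working it through.** **1. The plan's own figure.** Table 1 gives the sign items as tongue 8.3%, voice 6.7%, overall pulse 10% and cun pulse 16.7%. Their sum is 8.3 + 6.7 + 10 + 16.7 = 41.7%, which matches the sign weight in section 9.4.2. The inquiry items (cold frequency, sweating, aversion to wind and cold) carry 25 + 16.7 + 16.7 = 58.4%. The total of 100.1% is rounding.

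**2. What must hold for a rating to be affected.**

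| Step | What the documents show |
|---|---|
| The rater has the key | Yes, if the text of section 6.1.1 was in the version used on site (sections 6.1.1 and 10.1.5.1) |
| A lot number is visible on a container, returned pack or log | Not stated either way |
| The rater is the person who sees it | Not stated; sections 6.2.1 and 10.1.5.2 do not say who handles stock or keeps the log |
| The rating shifts as a result | Unknown |

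**3. Dates.** Section 5.5 plans enrolment from December 2018 to March 2019, and section 6.1.2 gives 84 days of treatment, so on plan ratings end around June 2019. The supplied text is V4.0 of 18 February 2022, about 32 months later, and its reference 10 is a 2021 paper. The documents do not show when the lot numbers entered the text.

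**4. Illustration of a score shift (assumed scenario).** Shift = sum of weight × change in item. One raw Table 2 level on all four signs gives 0.083 + 0.067 + 0.10 + 0.167 = 0.417. However, Table 2 runs 0–2 for overall pulse, 0–3 for tongue and cun pulse and 0–4 for voice, while the score is said to run 1–5, and no conversion is given. If each item were stretched to span 1–5, the same shift would be 0.10 × 4/2 + 0.083 × 4/3 + 0.167 × 4/3 + 0.067 × 4/4 = 0.60. The figure therefore depends on a scoring rule that is not stated.

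**5. Illustration of the false-positive rate (assumed inputs).** Take no true effect, 62 per arm (section 4.1), a two-sided 0.05 t-test, a fraction f of participants whose lot is recognised, and a rater shift of b SD between arms in those participants. The mean difference is f × b SD, with noncentrality f × b × √(62/2).

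| f | b = 0.2 | b = 0.5 |
|---|---|---|
| 0.10 | 5.1% | 5.9% |
| 0.25 | 5.9% | 10.6% |
| 0.50 | 8.6% | 28.2% |
| 1.00 | 19.7% | 78.9% |

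The documents give neither f nor b. The spread, from almost no harm to a useless test, shows that the size cannot be fixed from the plan.

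**The case against.** The strongest reply is that nothing in the plan shows unblinding. No lot number is placed on any container, returned pack or log, and nothing says that the practitioners who score participants handle stock. This stands, and it is why the point is conditional.

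The second reply is timing. If the planned dates were kept, V4.0 cannot be the text reviewed at the initiation meeting, and the lot numbers may have been added for the record after rating ended. This also stands. It changes what the sponsor should do, but it does not close the question, because the text is written prospectively and does not mark section 6.1.1 as a later addition.

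The third reply is that the severity score is not purely a matter of practitioner opinion. Inquiry items make up 58.4% of the weight and rest on what participants report, with fixed choices for sweating and aversion in Appendix 4. The signs have written anchors in Table 2, and tablets are matched in appearance, taste and coating (sections 4.2 and 6.2.2). This limits the exposure of the score. It does not help the traditional diagnosis, and matching tablets do not protect against a number that names the arm.

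**Conclusion.** The plan discloses a complete lot-to-arm key to people it says are blinded, and it describes nothing that keeps lot numbers from them. That is a weakness in the blind as written. The parts of the primary assessment most exposed are the sign items, at 41.7% of the PQD weight, and the whole of the traditional diagnosis.

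A reader might infer that the raters were in fact unblinded, or that the PQD score would be biased by 0.417. The documents support neither. The first needs a visible lot number, a rater who saw it and the key in the on-site version; none of these is documented. The second is an arbitrary scenario on unconverted item levels. What can be said is that if a rater holding this text saw a lot number, every participant known to have that lot would be decoded. How often that could happen, and with what effect, cannot be quantified.

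**What to change.** **If ratings are still to be made:** remove the lot-to-arm mapping from section 6.1.1 and keep it in a sponsor file closed to the site until database lock. State in section 6.2.2 that containers and site logs carry only a participant or kit code, which the sponsor links to the lot. Both parts are needed: with the key removed but lots still visible, participants would still fall into two recognisable groups, and opening one emergency envelope would identify both.

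**If ratings are complete:** state whether the version used on site carried the lot numbers, what labels, returned packs and dispensing logs showed, and which staff had access to them while ratings were made. Qualify the triple-blind claim to match the answer.

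**Cost:** a protocol edit, label text and a sponsor-held list linking codes to lots. The documents describe no kit-code system, so one may have to be set up; lot traceability is then kept through that list. In the second case the cost is a short statement in the report. The sample size and analysis do not change.
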